9.4. Rescue and Increased IOP Management

9.4.1. Criteria for Starting Rescue Medication

Any subject not responding adequately to the study drug at any time after randomization on POD1 may be rescued and placed on an appropriate alternative therapy determined by the Investigator. Subjects who, on examination of the anterior chamber, have one or more of the following criteria will be considered 'Rescued' subjects and should be discontinued from study drug dosing and placed on rescue mediation:

1. After randomization, anterior chamber cells count >30 cells.
2. After randomization, an increase in anterior chamber cell count by > 15 cells from POD1/pre-dose baseline.
3. After randomization, ≥ 2 grade of increase in anterior chamber flare from POD1/pre-dose baseline.

Initiation of rescue medication is at the discretion of the Investigator, following discussion with the Study Medical Monitor, even if none of the above criteria are met. However, it is recommended that the Investigator uses the above criteria to determine when to consider a subject for rescue medication.

Management

Investigators will use clinical judgment to determine the appropriate rescue medication to use and when to withdraw study drug and perform procedures.

While initiation of rescue medication is at the discretion of the Investigator, if one criterion above in Section 9.4.1 is met, the subject should be placed on rescue medication. Subjects not otherwise responding to study drug may be placed on alternative medication at the discretion of the Investigator even if none of the above criteria are met. In the situation where an investigator considers that alternative medication is required, but the above 'Rescue' criteria are not met, the subject is considered to be 'withdrawn' from the study and EOS assessments are to be performed. The choice of alternative medication is at the Investigator's discretion and will be used as directed by the Investigator. Any subject who is rescued based on the criteria in Section 6.3 and who is placed on rescue medication will discontinue the study drug and continue in the study for study assessments as described in Section 6.3.

A subject who is treated with an ocular corticosteroid or other anti-inflammatory product after POD22 (Part A) or POD15 (Part B) will be considered to be a 'Withdrawn' subject.

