Rescued subjects will be considered treatment failures, but the need for rescue medication will not be considered as an AE. Rescued or Withdrawn subjects experiencing an AE at the time of rescue/withdrawal will be followed through by the Investigator to stabilization or resolution of the AE or the end of the study (whichever comes last). Rescued/Withdrawn subjects should be followed to resolution of signs and symptoms of an AE or until the Investigator has deemed the subject is stable.

Note:

Clarification of the distinction between 'Rescued' and 'Withdrawn':

i) Process for 'Rescued' subjects:

- *The subject notifies the clinical site and is able to return for an unscheduled visit or scheduled visit before starting rescue medication.*
- *The subject has a visit and the investigator documents that the subject meets one of the rescue criteria. The subject should be rescued. The study drug is stopped and the subject should be started on the investigator's preferred rescue medication.*
 - *EOT assessments are completed at the time of this evaluation and the subject returns for the EOS assessments as shown in Table 5A or Table 5B.*

- *The subject's status is 'Rescued' and the reason for rescue must be one of the rescue criteria. This information is entered into the source and eCRF.*

ii) *Process for 'Withdrawn' subjects:*

- *The subject notifies the clinical site and is able to return for an unscheduled visit or scheduled visit. At the visit, the investigator's opinion is that the subject needs to be withdrawn because of inadequate control of inflammation and pain, but one or more of the rescue criteria are not met. The subject is withdrawn from the study, and at the investigator's discretion, the study drug is discontinued and alternative medication is started to treat the subject.*
 - *At this site visit, the EOS evaluation is completed.*
- *The subject attends the clinical site for a scheduled visit and the investigator considers that the subject is inadequately treated by the study drug, but one or more of the rescue criteria are not met. The subject is withdrawn from the study because of inadequate control of inflammation and pain, and at the investigator's discretion, the study drug is discontinued and alternative medication is used to treat the subject.*

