5.1.6.2. Missing data, rescue, last observation carried forward (LOCF)

LOCF	The last on study drug assessment is carried forward to impute a later missing value.
On study drug	Subjects are considered as being on study drug when they start their first dose until two days after their last dose of the study drug.

For efficacy analyses of POD1 to POD22 (Part A) and POD1 to POD15 (Part B), LOCF method will be used to impute all assessment values after the subjects that are rescued or early withdrawn and/or have stopped being on study drug to calculate mean, standard deviation, 95% confidence interval, median, Q1, Q3, minimum, and maximum for anterior chamber cell (ACC) count, ACC grade, ACF grade, pain grade, and Best Corrected Visual Acuity.

	Document Number: CLN.001.SAP	Version: 0
	Document Title: Clinical Study CPN-201 Statistical Analysis Plan	Page 16 of 35

Therefore, if a subject has an observed POD1 value for an efficacy endpoint, this subject should have observed or imputed values for the same endpoint through POD1 – POD22 for Part A or POD1-POD15 for Part B. Consequently, to avoid confusion, “POD22” will be used in place of “EOT” for Part A and “POD15” for Part B.

LOCF will not be used for “complete” subjects even if they have stopped study drug earlier than POD21 (Part A) and POD14 (Part B).

LOCF will not be used for safety analyses. For safety endpoints, the total number of subjects in the safety population and the summary statistics of all observed data will be calculated for each active dosing regimen and its matching vehicle placebo group for each visit.

Since the eye exams at Screening and EOS visits are evaluated as safety endpoints, the last non-missing observation from the study-eye at post-surgery PODs will not be carried forward to impute missing values at EOS visit for the Screening vs. EOS analyses.

To be clear, in any cases, EOS measurements will not be modified and Screening measurements will not be carried forward.

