5.3. Primary and Secondary Efficacy Endpoint(s) Analysis

5.3.1. Definition of Primary and Secondary Efficacy Endpoint(s)

The **primary efficacy endpoints** are:

- Anterior chamber cell (ACC) count at POD15 (mean of two counts)
- Pain grade at POD15

Pain grade is defined as follows:

0	None: Absence of pain.
1	Minimal: Presence of minimal throbbing or aching pain (expected following cataract surgery)
2	Mild: Presence of mild throbbing or aching pain, easily tolerated.
3	Moderate: Presence of moderate throbbing or aching pain leading to the desire to use an analgesic.
4	Moderate: Presence of moderate throbbing or aching pain leading to the desire to use an analgesic.

The **secondary efficacy endpoints** are:

- Anterior chamber cell (ACC) count at PODs 4, 8 (and 22 for Part A), mean of two counts at each POD.
- ACC grade at PODs 4, 8, 15 (and 22 for Part A), mean of two grades at each POD

ACC grade is defined as the following:

0	1	2	3	4
0 cell	1-5 cells	6-15 cells	16-30 cells	> 30

- Pain grade at PODs 4, 8 (and 22 for Part A)
- ACF grade at PODs 4, 8, 15 (and 22 for Part A)

ACF grade is defined as follows:

ACF Grade	ACF Grade Used for Analyses	Description

	Document Number: CLN.001.SAP	Version: 0
	Document Title: Clinical Study CPN-201 Statistical Analysis Plan	Page 19 of 35

0	0	None
1+	1	Faint
2+	2	Moderate (iris and lens details clear)
3+	3	Marked (iris and lens details hazy)
4+	4	Intense (fibrin or plastic aqueous)

- Use of rescue medication and/or early withdrawal
- Proportion of subjects with ACC count = 0 (first measurement only) at PODs 4, 8, 15 (and 22 for Part A) without receiving rescue medication;
- Proportion of subjects who are pain-free at PODs 4, 8, 15 (and 22 for Part A) without receiving rescue medication;
- Proportion of subjects with ACF grade = 0 at PODs 4, 8, 15 (and 22 for Part A) without receiving rescue medication
- Visual acuity (ETDRS Best corrected Visual Acuity by pinhole method) at PODs 4, 8, 15 (and 22 for Part A) without receiving rescue medication

See Section 7.2 of the protocol for more details about the definitions of the endpoints.

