ACC count, ACC grade, pain grade, ACF grade, and ETDRS acuity (logMAR score) will be summarized descriptively in [Tables 14.2.2.2.1-14.2.2.2.4](#), and [14.2.5.2](#) for POD1-22 (Part A) and POD1-15 (Part B) by each active dosing regimen and its matching vehicle placebo. LOCF method will be used to impute all assessments after the subject stopped being on study drug to calculate mean, standard deviation, 95% confidence interval, median, Q1, Q3, minimum, and maximum. On study drug is defined in Section 5.1.6.2.

The observed data (without LOCF or any other imputation) when the subjects are still on study drug of above listed endpoints will also be summarized in [Tables 14.2.2.3.1 – 14.2.2.3.4](#), and [14.2.5.3](#). The treatment difference will also be reflected by the number of subjects that are still on study drug. PODs defined by [Table F](#) will be used for calculating the treatment group statistics.

	Document Number: CLN.001.SAP	Version: 0
	Document Title: Clinical Study CPN-201 Statistical Analysis Plan	Page 21 of 35

The same statistics will be calculated for CFB of the same endpoints, with POD1 pre-dose measure as the baseline, in [Tables 14.2.2.4.1-14.2.2.4.4](#), and [14.2.5.4](#). LOCF will be used to impute missing values and all assessments after subjects stopped being on study drug. Statistical comparison between each active dosing regimen and its matching vehicle placebo will be carried out for each visit during POD4 - POD22 (Part A) and POD4 – POD15 (Part B) using t-test and Mann-Whitney non-parametric tests noting that p-values will only be considered descriptive and hypothesis-generating.

These endpoints will also be visually presented in [Figures 14.2.2.1, 14.2.2.2, 14.2.5.1](#), and [14.2.5.2](#).

The distribution of ACC, pain, and ACF over different grades for each treatment will be described by the frequency and proportion of subjects within each grade for each active dosing regimen and its matching vehicle placebo for each visit during POD4 – POD22 (Part A) and POD4 – POD15 (Part B) in the lower part of [Tables 14.2.3.1 – 14.2.3.3](#) without LOCF. The denominator of the proportion is the number of subjects randomized. The treatment difference will also be reflected by the number of subjects that are still on study drug.

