The proportion of subjects with ACC count = 0, pain-free, or ACF grade = 0 without receiving rescue medication will be calculated for each active dosing regimen and its matching vehicle placebo for each visit during POD1 – POD22 (Part A) and POD1 – POD15 (Part B) in [Table 14.2.4](#) and [Figure 14.2.4](#). The denominator will be the total number of subjects randomized in each treatment group. LOCF will be used to impute missing values and all assessments after subjects stopped being on study drug.

All subjects' inflammation and pain information will be presented in [Listing 16.2.6.2](#) and best correct visual acuity information will be presented in [Listing 16.2.6.3](#).

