16	“LOCF will not be used for “complete” subjects even if they have stopped study drug earlier than POD21 (Part A) and POD14 (Part B).”	Removed from SAP.	The change reflects the intended purpose of the LOCF analysis.
21	For changes from baseline of ACC count, ACC grade, pain grade, ACF grade, and ETDRS acuity (logMAR score), statistical comparison between each active dosing regimen and its matching vehicle	
 1. The comparison was carried out for the means of the efficacy endpoints as well. 2. For efficacy endpoints, the Pearson-Chi-Square test was used to compare the proportions of 	New Exploratory analyses added.

	Document Number: CPN-201.SAP Appendix Document Title: Clinical Study CPN-201 Statistical Analysis Plan Follow-Up	Version: 1 Page: 4 of 5
--	---	--

	
placebo will be carried out for each visit during POD4 - POD22 (Part A) and POD4 – POD15 (Part B) using t-test and Mann-Whitney non-parametric tests.
	
“resolved” subjects (‘Sustained’ Grade = 0) between each active group and its matching placebo group at POD4 and sustained at all later visits.
 
3. IOP means and changes from baseline were compared between active treatment groups and their matching placebo groups.
	
21	
Sensitivity Analyses:
 
“A subset of efficacy analyses will be examined for the per-protocol population as supportive analysis.”
	
These analyses will not be conducted.
	
Only 5 out of 132 (3.8%) subjects were excluded from Per Protocol population because of protocol deviations. The differences from the LOCF analyses of efficacy endpoints will be negligible.

21	
Sensitivity Analyses:
 
“Since only first ACC count will be used to define the proportion of subject with ACC count = 0,
	
These analyses will not be conducted.
	
The analyses will use the first ACC count - this is comparable to real-world clinical practice. Because only 6 (4.5%) subjects had

	Document Number: CPN-201.SAP Appendix Document Title: Clinical Study CPN-201 Statistical Analysis Plan Follow-Up	Version: 1 Page 5 of 5
--	---	---

	
analyses of using second ACC count and/or a combination of the two counts will be explored.”
		
different ACC counts at a visit, the other analyses are redundant.

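### LOCF after rescue can give a protocol-defined treatment failure the best score on the primary POD15 pain endpoint, because no rescue criterion involves pain; a worst-rank analysis should stand beside it

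*SAP*

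**What the plan says.** **Endpoints.** SAP 5.3.1 names two primary efficacy endpoints: ACC count at POD15 (the mean of two counts) and pain grade at POD15.

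**Handling of rescue.** SAP 5.1.6.2 provides that "LOCF method will be used to impute all assessment values after the subjects that are rescued or early withdrawn". The last on-drug "assessment is carried forward to impute a later missing value", and a subject counts as on drug until two days after the last dose. For change from baseline, SAP 5.3.2 adds that "LOCF will be used to impute missing values and all assessments after subjects stopped being on study drug", and compares arms at each visit by t-test and Mann-Whitney. The SAP Appendix (section 2, Modifications) extends testing to the endpoint values: "The comparison was carried out for the means of the efficacy endpoints as well".

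**Who is rescued.** Protocol 9.4.1 lists three criteria. The first is "After randomization, anterior chamber cells count >30 cells"; the others are a rise of more than 15 cells from baseline and a flare increase of at least two grades. SAP 5.3.2 repeats the list. Pain is not among them.

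**Status of rescued subjects.** Protocol 9.4.1: "Rescued subjects will be considered treatment failures, but the need for rescue medication will not be considered as an AE". Sections 5.4.1 and 8.1 say the same.

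**Where failure status is used.** In SAP 5.3.2, "The proportion of subjects with ACC count = 0, pain-free, or ACF grade = 0 without receiving rescue medication will be calculated", over all randomized subjects. Table 14.2.1 counts rescues by reason and early withdrawals. Under SAP 5.3.4.1 a subject who stops drug early can never be classed as resolved.

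**The concern.** A subject rescued for more than 30 cells who happens to report no pain is a treatment failure under the protocol. In the primary pain mean and tests the same subject is carried to POD15 as grade 0, the best value on the scale. The pain-free proportion, by contrast, requires that no rescue medication was received. Subjects withdrawn because inflammation and pain were inadequately controlled are handled by the same LOCF rule.

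The study exists to choose a regimen for Phase 3 (SAP section 1) with about 21 subjects per arm. If rescue is more common on vehicle, carrying zeros for rescued vehicle subjects moves the vehicle pain mean towards active. The pain comparison then depends partly on what a subject happened to report at the moment of rescue for something else.

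**Working it through.** **1. Planning figure.** SAP section 3 plans 21 per arm for about 20 completers at 5% dropout: 20/0.95 = 21.05, so it reproduces. Neither document states an expected rescue rate or a power.

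**2. What is carried to POD15.** Protocol 9.4.1 has the EOT assessments, which include pain, done at the rescue visit. That visit falls within the on-drug period, so its values are eligible.

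| Rescue trigger | Pain carried | ACC carried, before averaging |
|---|---|---|
| More than 30 cells | any grade, including 0 | above 30 |
| Rise of more than 15 | any grade, including 0 | at least 11 + 16 = 27 (baseline must exceed 10) |
| Flare only | any grade, including 0 | 0 up to the lower of 30 and baseline + 15 |
| Discretionary, no criterion met | any grade, including 0 | a low count is possible |

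SAP 5.1.9 averages two visits in one window. A scheduled count of 5 and a rescue count taken as 31 (an assumed number, since the count is recorded only as above 30) give (5 + 31)/2 = 18. A low or diluted ACC therefore needs flare-only rescue, discretionary rescue or window averaging.

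**3. Leverage of one subject.** Scoring a rescued subject 4 instead of a carried 0 moves the arm mean by 4/21 = 0.19 grade.

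**4. Illustration for pain.** All inputs are assumptions: 21 per arm; rescue 40% vehicle, 10% active; half of rescued subjects at pain 0 and the rest spread evenly over grades 1 to 3; non-rescued pain P(0,1,2,3) = (0.65, 0.25, 0.08, 0.02) in both arms. Expected vehicle failures carried as 0: 21 × 0.40 × 0.50 = 4.2.

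*Worst rank.* Probability that an active subject does better, counting ties as half: 0.9 × 0.4 + 0.5 × (0.6 × 0.9 + 0.4 × 0.1) = 0.36 + 0.29 = 0.65. This equals 0.5 + 0.5 × (0.40 − 0.10), so in this scenario it is driven wholly by the rescue difference.

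*LOCF.* The mixed grade distributions are (0.590, 0.217, 0.115, 0.079) on vehicle and (0.635, 0.242, 0.089, 0.035) on active. Active is strictly better with probability 0.314 and tied with probability 0.440, giving 0.314 + 0.220 = 0.534. Simulation gives about 0.54.

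**5. Share of simulated trials with Mann-Whitney p<0.05.**

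| Assumed scenario | LOCF | Worst rank |
|---|---|---|
| 40% v 10% rescue, half at pain 0 | about 8% | about 46% |
| 30–50% v 5–10%, with 30–70% at pain 0 | about 4–23% | about 23–82% |
| 10% v 5% | about 4–5% | about 5–7% |
| 20% in both arms, true pain difference (vehicle non-rescued 0.35, 0.35, 0.20, 0.10) | about 36% | about 24% |

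**The case against.** Much can be said for the plan, and most of it stands.

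- **A reader might infer that the SAP contradicts the protocol.** It does not. Protocol 10.6 itself orders LOCF from the last pre-rescue value for ACC and leaves other missing data to the SAP. For ACC the tension with the treatment-failure rule lies inside the protocol. For pain the SAP uses discretion it was given, although its choice does not carry out the failure rule.
- **A reader might infer that cell counts are equally affected.** Rescue for cells carries a bad count, as it should; only the routes in step 2 allow a low one.
- **A reader might infer that LOCF hides a pain effect.** The first three scenarios contain no pain difference among non-rescued subjects. LOCF staying near 5% in most of them is not a failure to detect one. The higher worst-rank figures largely detect the assumed rescue difference, which Table 14.2.1 already shows.
- **Failure status is reported elsewhere:** rescue counts, rescue-free proportions and the resolved analysis, to which the SAP Appendix adds a chi-square test. A mean pain grade and a rescue-adjusted proportion answer different questions.
- **Substantial rescue is not documented.** The documents do not say that rescue will fall mainly on vehicle. Read literally, planning for about 20 of 21 to complete dosing implies few rescues.

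What remains is that no planned analysis of the primary pain mean or test treats rescue as failure.

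**Conclusion.** The point holds for pain grade and in limited form for ACC count. A subject whom the protocol calls a failure can be scored 0 in the primary POD15 pain mean and tests, and nothing in the SAP offsets this within those analyses.

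The size is conditional. It is material only with a substantial rescue imbalance: 0.54 v 0.65 for the probability of a better outcome at an assumed 40% v 10%. It is negligible at 10% v 5%, and the ranking of the methods reverses when rescue is balanced and pain truly differs. Rescue rates and pain distributions are assumptions throughout.

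Two stronger conclusions are unsupported. First, worst rank should not replace LOCF as the lead analysis; that is a choice of estimand with losses as well as gains. Second, there is no type I error issue: the documents test no formal hypotheses, treat p-values as exploratory, and do not call the two endpoints co-primary. This is a cheap improvement to the readout.

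**What to change.** In SAP 5.3.2, beside the LOCF analysis, add the planned Mann-Whitney for POD15 pain grade and ACC count with subjects rescued, or withdrawn for inadequate control, given a common worst rank. Report the probability of a better outcome on active with a 95% CI. Place the rescue and withdrawal counts from Table 14.2.1 next to it, and interpret pain from both analyses. State in the SAP what each result estimates.

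Before coding, reconcile two parts of Protocol 9.4.1. One allows rescue medication when no criterion is met; another classes a subject given alternative medication in that situation as withdrawn. The worst-rank group should be defined from the reconciled text.

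The cost is SAP wording and one recode before an existing test. No new data are needed, since rescue and the reason for withdrawal are already captured in the eCRF. The downside is that the ranked result is a composite of pain (or cells) and rescue, and can be less sensitive to pain alone when rescue is balanced.

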5.1.7. Baseline Definitions

Baseline is the last observed (without LOCF or any other imputation) assessment prior to the time when the first dose of study drug is administered unless otherwise specified.

Screening will be considered as the baseline for the Screening vs EOS comparison. EOS data will be summarized with Screening data in the same table.

For all other PODs, i.e., POD 1, 4, 8, 15, and 22 (for Part A), POD1, 4, 8, and 15 (for Part B), ocular examinations are carried out for the study eye only. These data will be summarized in the same table for each active dosing regimen and its matching vehicle placebo. The Pre-dose assessment at POD1 will be the baseline.

5.1.8. Change from Baseline

Change from baseline (CFB) is calculated as:	$\text{CFB value} = \text{‘visit’ value} - \text{baseline value}$ 
CFB will be indicated as missing, if either the baseline or post-dose value is missing.

--	--

	Document Number: CLN.001.SAP	Version: 0
	Document Title: Clinical Study CPN-201 Statistical Analysis Plan	Page 17 of 35

5.1.9. Multiple Assessments at One Time Point

Where multiple assessments are recorded for a particular POD, e.g., ACC counts at the same visit or when two visits fall in the same POD window ([Table F](#)), the mean of the assessments will be calculated and used in any derivation of summary statistics. All observed data will be listed.

Note, for any efficacy endpoint:

If EOS falls in the same POD window ([Table F](#)) with another visit, the assessment obtained from that other visit, while the subject is still on study drug, will be used for the efficacy analyses.

If there are no other assessments in the same POD window ([Table F](#)) while the subject is still on study drug, e.g., within 2 days of the last dose of study drug as defined in 5.1.6.2, the EOS assessment will be used for efficacy analyses.

For any safety categorial endpoint, instead of taking the mean of all assessments within that POD window, the assessment obtained at the latest visit within that POD window will be used for that POD.

EOS assessments will not be modified in any case as mentioned in 5.1.6.2.

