6.2.7. Subject Early Termination

Subjects who are terminated from the study early, but the rescue criteria in Section 9.4.1 are not met, should have POD28/EOS (Part A) or POD22/EOS (Part B) assessments performed at the time of termination, or as soon thereafter as possible. At early termination the ocular assessments are to be performed on both eyes.

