6.3. Study Visit Schedule for Rescued Subjects

Subjects who meet the criteria for rescue presented in Section 9.4 should discontinue study drug and receive rescue medication. Subjects who are rescued should continue in the study as indicated in Table 5A or Table 5B below. Note that the assessments in the check box under each visit in the Schedule of Events (Table 2A or Table 2B) with a (R) next to “X” indicates that the assessments should be performed on rescued subjects at the indicated visits. Table 5A or Table 5B provides an overview of the study visits and assessments required for rescued subjects depending on when the rescue occurs during the study. It is important to note that (i) subjects rescued on or before POD16 in Part A will be considered as having completed the study before POD28 as indicated by ‘na’ in Table 5A and (ii) subjects rescued on or before POD9 in Part B will be considered as having completed the study before POD22 as indicated by ‘na’ in Table 5B.

Table 5A: Visits for Rescued Subjects (Part A)

Time of Rescue	Protocol Defined Study Visits				
	POD4 (± 1 day)	POD8 (± 1 day)	POD15 (± 1 day)	POD22 (± 1 day)	POD28 (± 1 day)
PODs 2-5	Conduct EOT (POD22) assessments at time of rescue but no later than POD4/5	Complete POD8 assessments in Table 2A marked with an (R)	Complete EOS (POD28) assessments and terminate subject from the study	na	na
PODs 6-9	per protocol	Conduct EOT (POD22) assessments at time of rescue but no later than POD7/8/9	Complete EOS (POD28) assessments and terminate subject from the study	na	na
PODs 10-16	per protocol	per protocol	Conduct EOT (POD22) assessments at time of rescue but no later than POD14/15/16	Complete EOS (POD28) assessments and terminate subject from the study	na
PODs 17-22	per protocol	per protocol	per protocol	Complete EOT (POD22) assessments at time of rescue but no later than POD22/23	Complete EOS (POD28) assessments and termination subject from the study

na = not applicable

Table 5B: Visits for Rescued Subjects (Part B)

Time of Rescue	Protocol Defined Study Visits			
	POD4 (± 1 day)	POD8 (± 1 day)	POD15 (± 1 day)	POD22 (± 1 day)
PODs 2-5	Conduct EOT (POD15) assessments at time of rescue but no later than POD4/5	Complete POD8 assessments in Table 2B marked with an (R)	Complete EOS (POD22) assessments and terminate subject from the study	na

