PODs 6-9	per protocol	Conduct EOT (POD15) assessments at time of rescue but no later than POD7/8/9	Complete EOS (POD22) assessments and terminate subject from the study	na
PODs 10-16	per protocol	per protocol	Conduct EOT (POD15) assessments at time of rescue but no later than POD15/16	Complete EOS (POD22) assessments and terminate subject from the study

na = not applicable

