5.1.5.2 Visit windows

It is expected that all visits should occur according to the protocol schedule described in [Table C1](#) and [Table C2](#), the Schedule of Events; visits outside of this schedule will be addressed as protocol deviations. A new visit variable, AVISIT, will be defined based on the visit date relative to the date of surgery and a windowing strategy described by [Table F](#). AVISIT will only be used for efficacy variables.

Table F: Windowing Strategy:

Surgery	Day 1 post-surgery	2-6 days post-surgery	7-11 days post-surgery	12-18 days post-surgery	19-25 days post-surgery	26+ days post-surgery
Day 0	POD1	POD4	POD8	POD15	POD22	POD28

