6.6. Changes to Protocol-Planned Analyses

- Added analyses for ACC grade at PODs 4, 8, 15 (and 22 for Part A).

	Document Number: CLN.001.SAP	Version: 0
	Document Title: Clinical Study CPN-201 Statistical Analysis Plan	Page 28 of 35

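### SAP 5.1.9 conflicts with the LOCF rule: read literally, it takes a post-rescue end-of-study value as the POD15 result for subjects rescued on PODs 2-9

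*SAP*

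**What the plan says.** The primary efficacy endpoints are ACC count and pain grade at POD15 (SAP 5.3.1).

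- **Window rule.** SAP 5.1.5.2: "A new visit variable, AVISIT, will be defined based on the visit date relative to the date of surgery and a windowing strategy" set out in Table F. Days 12-18 are POD15 and days 19-25 are POD22.
- **EOS rule.** SAP 5.1.9 applies to any efficacy endpoint. If EOS shares a window with another on-drug visit, the other visit is used. If there is no such visit, the text reads "within 2 days of the last dose of study drug as defined in 5.1.6.2, the EOS assessment will be used for efficacy analyses". The section closes by saying that EOS values are never modified. It mentions neither rescue nor LOCF.
- **LOCF rule.** SAP 5.1.6.2: "LOCF method will be used to impute all assessment values after the subjects that are rescued or early withdrawn", and likewise once a subject is no longer on study drug. ACC count and pain grade are both named. On-drug status lasts until two days after the last dose. SAP 5.3.2 repeats the rule for the study-eye summaries and changes from baseline. Protocol 10.6 has the corresponding rule for ACC after rescue.
- **Visits after rescue.** In Protocol 6.3, the POD15 column for rescue on PODs 2-9 reads "Complete EOS (POD28) assessments and terminate subject from the study" in Table 5A (Part A) and "Complete EOS (POD22) assessments and terminate subject from the study" in Table 5B (Part B).

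**The concern.** Two SAP rules give different POD15 values for the same subject. One takes the EOS value, recorded after rescue medication has started. The other takes the last on-drug value, normally recorded at the rescue visit. The protocol counts rescued subjects as treatment failures, and a rescue-treated value could make them look controlled in the primary means. Two programmers working from this SAP could both defend their derivations and still report different arm means. The SAP gives regimen selection for Phase 3 as the study's purpose, so the estimates matter even though the p-values are descriptive.

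**Working it through.** The plan states no figure to reproduce. The check is of timing, followed by an illustration of size.

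**Step 1: does the literal condition apply?** Study drug stops at rescue (Protocol 6.3, 9.4.1). Assume the last dose is on the rescue day, the latest possible. On-drug status then ends on rescue day + 2.

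| Part | Rescue day | EOS days (Tables 5A/5B) | Table F window | On-drug ends by | Efficacy time point? |
|---|---|---|---|---|---|
| A and B | 2-9 | 14-16 | POD15 (12-18) | 9 + 2 = 11 | Yes, primary |
| A | 10-16 | 21-23 | POD22 (19-25) | 16 + 2 = 18 | Yes, secondary |
| B | 10-16 | 21-23 | POD22 (19-25) | 18 | No |
| A | 17-22 | 27-29 | POD28 (26+) | 22 + 2 = 24 | No |

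In the first two rows on-drug status ends before the window opens (11 < 12; 18 < 19). No on-drug assessment can exist in the window, so the literal condition is always met. The EOS value selected is at least 14 - 9 = 5 days (row 1) or 21 - 16 = 5 days (row 2) after the last dose. Table 2B allows only +1 day for POD15 in Part B; days 15-16 give the same result.

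**Step 2: which outputs are exposed?** The LOCF means, the changes from baseline and their descriptive tests. The observed-data tables are restricted to on-drug values, and the proportions with ACC = 0, no pain or flare = 0 already require no rescue medication (SAP 5.3.2).

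**Step 3: size, illustration only.** The shift in an arm mean per rescued subject is (L - E)/n, where L is the carried-forward ACC, E the EOS ACC and n the arm size. The documents give no rescue rates and no post-rescue counts. Assume E = 0 to 10, with n = 21 as planned.

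| L | Basis | E = 10 | E = 0 |
|---|---|---|---|
| 31 | Rescue for more than 30 cells, taken as 31 (the actual count is not recorded) | 21/21 = 1.00 | 31/21 = 1.48 |
| 27 | Baseline 11, rise of 16 | 17/21 = 0.81 | 27/21 = 1.29 |
| 19 | Mean of 27 and an earlier 11 | 9/21 = 0.43 | 19/21 = 0.90 |
| 13.5 | Mean of 27 and an earlier 0 | 3.5/21 = 0.17 | 13.5/21 = 0.64 |
| 10 | Flare-only rescue, assumed count | 0 | 10/21 = 0.48 |

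The rows for 19 and 13.5 assume that an earlier visit falls in the same window as the rescue visit and that LOCF carries the average (SAP 5.1.9: "the mean of the assessments will be calculated and used in any derivation of summary statistics"). If LOCF carries the single last assessment, 27 applies.

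The SAP Appendix reports 132 subjects. If they are spread equally over six arms, n = 132/6 = 22 and the shifts are 17/22 = 0.77 to 27/22 = 1.23 for L = 27, and 21/22 = 0.95 to 31/22 = 1.41 for L = 31.

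For pain, an assumed fall of 1 to 4 grades after rescue gives 1/21 = 0.05 to 4/21 = 0.19 grade.

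**Step 4: arm difference.** With the same shift per subject, the difference changes by that shift times the excess of rescues in one arm. It is 0 if rescues are equal. For L = 27 it is 0.81-1.29 cells for one extra rescue and 3 x 17/21 = 2.43 to 3 x 27/21 = 3.86 for three.

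**The case against.** The strongest reply is that the SAP, read as a whole, already requires LOCF.

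- SAP 5.1.6.2 and 5.3.2 do more than fill gaps. They replace every assessment after rescue or off drug, so an EOS value picked by 5.1.9 can be overwritten afterwards.
- Subjects rescued on PODs 2-5 also have a post-rescue POD8 visit, which 5.1.6.2 replaces. LOCF at POD8 followed by a rescue-treated value at POD15 would be incoherent.
- The on-drug phrase in 5.1.9 can be read as describing the EOS assessment itself. The sentence then serves withdrawn subjects, who under Protocol 6.2.7 have EOS "assessments performed at the time of termination, or as soon thereafter as possible" and so can still be on drug. It never reaches subjects rescued on these days.
- SAP 6.6 lists one change from the protocol's analyses, the addition of ACC grade, and no departure from Protocol 10.6.
- The statement that EOS values are not modified follows the Screening-versus-EOS paragraph in 5.1.6.2 and fits that safety comparison.

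These arguments make LOCF very likely the intent. They do not settle the wording. The grammar of 5.1.9 attaches the on-drug phrase to the other assessments, the rule covers any efficacy endpoint, and neither section says which prevails. The short definition of LOCF in 5.1.6.2 speaks of a later missing value, which leaves room for the view that an assigned EOS value is not missing.

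A reader might infer that pain has no LOCF rule because Protocol 10.6 covers only ACC. It has one: 5.1.6.2 names pain grade. A reader might also infer that the SAP Appendix kept the EOS rule on purpose when it deleted the sentence exempting complete subjects from LOCF. The Appendix is silent on 5.1.9, and its stated reason for the deletion points towards LOCF.

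**Conclusion.** The conflict is real and minor. Read literally, 5.1.9 selects a post-rescue value at POD15 for every subject rescued on PODs 2-9 in both parts, and at POD22 in Part A for rescue on PODs 10-16. That contradicts SAP 5.1.6.2 and 5.3.2 and, for ACC, Protocol 10.6, with no order of precedence.

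The documents do not support the stronger conclusion that the plan prescribes rescue-treated values for the primary endpoints, since LOCF is the better reading of the whole. Nor do they show that any result was derived that way.

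The size cannot be known without rescue rates. On the assumptions above, each affected subject moves an arm mean by at most about 1.3 cells (27 carried forward) or 1.5 cells (31 carried forward), and by less for lower carried values. The treatment difference moves only with unequal rescue counts, or with unequal shifts per subject. No formal hypotheses are tested, so the issue is bias in descriptive estimates, not type I error. Rescue counts by reason are tabulated, so a reader could partly judge the effect.

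**What to change.** Add three statements to SAP 5.1.9:

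1. An EOS assessment enters an efficacy analysis only if it was made on study drug (no more than two days after the last dose) and before any rescue or alternative anti-inflammatory medication.
2. In all other cases LOCF under 5.1.6.2 governs.
3. The rule against modifying EOS values concerns only the Screening-versus-EOS tables.

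The SAP Appendix describes some comparisons in the past tense. If the analyses have already been run, the study report should say which derivation was used for subjects rescued on PODs 2-9 and, for POD22 in Part A, on PODs 10-16.

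The cost is a few SAP sentences and one programming condition, or one sentence of disclosure. No new data are needed and no clinical procedure changes.
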